2.3.3 Exploratory Efficacy Endpoints

The exploratory efficacy endpoints include comparison between results in patients receiving PSL versus placebo for the following:

- Change in eGFR by Modified Dose in Renal Disease (MDRD) formula.
- Changes from baseline in levels of donor-specific anti-HLA antibodies.

- Proportion of patients with resolution of BK viremia at 8 weeks post virus-specific T cell infusion.
- Proportion of patients with eGFR >20 mL/min at 24 weeks.
- Incidence of new target viral infections or recrudescent infections (i.e., BKV, CMV, EBV, AdV, JCV, and/or HHV-6) as defined by onset of viremia and/or the presence of associated symptoms relative to baseline.
- Length of BKV remission (i.e., time from clearance of BK viremia to reappearance of BK viremia (plasma viral load >156 copies/mL \times 2 measures that are at least 2 weeks apart) or end of study).
- Number of patients with screening BK viremia < 10,000 copies/mL who develop BK viremia \geq 10,000 copies/mL (sustained or non-sustained) or who experience a medically significant event that leads to changes in immunosuppression reduction.
- The absolute viral load in patients in the investigational arms versus that in patients in the placebo arm with screening BK viremia <10,000 copies/mL.

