3.4 Efficacy Analyses

This section describes the analysis to be conducted for the key secondary, other secondary and exploratory efficacy endpoint along with other endpoints. The efficacy analysis will be performed on the ITT population unless otherwise stated. Analyses using mITT may be set aside if it is determined that the ITT population and the mITT Population are identical. Unless otherwise specified, the results of efficacy analysis and all the summary tables will be presented by stratum and treatment group.

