3.4.2 Exploratory Efficacy Endpoints

Observed results, change from Baseline, and percent change from baseline for eGFR estimated by MDRD and creatinine will be summarized by visit using descriptive statistics.

Donor specific anti-HLA antibodies (DSA) (yes/no) will be summarized by visit using descriptive statistics.

Resolution of viremia will be generally defined as achieving a post-baseline viral load measure below the lower limit of quantification (<LLOQ) for that viral assay. The number of patients with resolution for each virus (BKV, CMV, EBV, AdV, JCV, and/or HHV-6) will be summarized by visit and at any visits. In addition, the proportion of patients reaching at least 1 log10 reduction or <LLOQ in BK viral load post infusion will be summarized by visit and at any visits.

LLOQ values for the viruses of interest are:

BKV Viral Load (Copy/mL): LLOQ = 156

Non-BK Target Viruses:

ADV Viral Load (Copy/mL): LLOQ = 32

CMV Viral Load (Copy/mL): LLOQ = 65.6

EBV Viral Load (Copy/mL): LLOQ = 37

HHV-6 Human Herpesvirus 6 (Copy/mL): LLOQ = 110

JCV JC Virus (IU/mL): LLOQ = 76

Time-to-event endpoints will be summarized using the Kaplan-Meier method. Number of patients with events and number of patients censored and reason of censoring will be presented along with estimate for the median time (days) and its 95% CI. Time-to-event will be presented using Kaplan-Meier plots.

Time to resolution of BK viremia will be calculated as starting at randomization for patients with detectable virus and ending at the first undetectable viral load (i.e., <LLOQ). Patients who discontinued from the study early or deceased before they are observed to have achieved resolution will be censored at the last assessment date for this endpoint.

For patients who reach the resolution of BK viremia, time to reappearance of BK viremia (duration of viral remission) will be calculated as starting at the first assessment with undetectable viral load and ending at the first detectable viral load (confirmed with 2 consecutive measures at least 8 days apart, or end of study if only one measure is available). Patients not demonstrating the reappearance of viremia would be censored on the date of the latest assessment for this endpoint. Patients who discontinued from the study early or deceased before they are observed to have will be censored at the last assessment date for this endpoint.

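### Duration of BK remission is shown by arm only among patients who cleared, so the PSL-placebo contrast is not randomized and could be biased in either direction

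*SAP*

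**What the plan says.** SAP 3.4.2 defines the analysis set and the clock for remission. The set: "For patients who reach the resolution of BK viremia, time to reappearance of BK viremia (duration of viral remission) will be calculated". The clock: "starting at the first assessment with undetectable viral load and ending at the first detectable viral load", with reappearance to be confirmed. Patients without reappearance are censored at their last assessment. The method is stated in the same section: "Time-to-event endpoints will be summarized using the Kaplan-Meier method", giving a median, its 95% CI and a plot. Table 1 in SAP 3.4.3 lists the endpoint again with Kaplan-Meier.

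SAP 2.3.3 places this endpoint, described as "Length of BKV remission (i.e., time from clearance of BK viremia to reappearance of BK viremia" or end of study, in a list introduced by "The exploratory efficacy endpoints include comparison between results in patients receiving PSL versus placebo for the following".

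Two general rules in SAP 3.4 bear on it. On the population: "The efficacy analysis will be performed on the ITT population unless otherwise stated". On display, unless otherwise specified, "the results of efficacy analysis and all the summary tables will be presented by stratum and treatment group". The strata are defined by screening BK load (Protocol 9.2); the cut is redacted in the public documents.

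The SAP names no test, hazard ratio or covariate adjustment for remission duration. Nor does it caution that the by-arm curves rest on a subset formed after randomization.

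**The concern.** Randomization makes the arms comparable at entry. It does not make the clearers in one arm comparable with the clearers in the other. The trial's own hypothesis is that PSL suppresses BK viral load better than placebo. If that is true and more PSL patients clear, the PSL clearers are a mixture: patients who would have cleared anyway, plus patients who cleared only because of PSL. The placebo clearers contain only the first kind. If the two kinds relapse at different rates, the curves separate even when PSL has no effect on relapse.

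What is at stake is how the durability display is read. A Kaplan-Meier plot with one curve per arm, under an endpoint listed as PSL versus placebo, will be taken as evidence about how long PSL remissions last. In a proof-of-concept study that is also meant to inform the dosing interval (Protocol 4.2), an apparent deficit or advantage produced by selection alone could mislead later planning.

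**Working it through.** The plan states no clearance rate, relapse rate, event count or power for this endpoint, so there is no figure to reproduce. The check asks whether the mechanism can operate here, which way it can run, and what the stratified presentation does to it.

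**Inputs from the documents.** Three arms of 20 (Protocol 9.2, SAP 2.2.3), hence pooled PSL 40 versus placebo 20. Entry load 350 to 10,000,000 copies/mL (Protocol 5.1). LLOQ 156 copies/mL (SAP 3.4.2). All clearance and relapse rates below are assumptions.

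**Step 1: how unequal is the task of clearing?** The fall needed to reach LLOQ is log10(load/156):
- 350 copies/mL: log10(350/156) = 0.35
- 10,000 copies/mL: log10(10,000/156) = 1.81
- 10,000,000 copies/mL: log10(10,000,000/156) = 4.81

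The required fall varies by almost 4.5 log10 across eligible patients, so who clears is likely to depend on patient characteristics.

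**Step 2: two kinds of patient.** Assume a share pE = 20% clears on either arm (easy) and a share pH = 20% clears only on PSL (hard). Let rE and rH be their 12-week relapse risks without drug effect. A relapse hazard ratio HR on PSL changes each risk r to r' = 1 − (1 − r)^HR.
- Relapse among clearers: placebo rE; PSL (pE·rE' + pH·rH')/(pE + pH).
- Cleared and not relapsed, all randomized: placebo pE(1 − rE); PSL pE(1 − rE') + pH(1 − rH').

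| rE, rH, HR | Relapse among clearers, placebo vs PSL | Cleared and not relapsed, all randomized, placebo vs PSL |
|---|---|---|
| 10%, 40%, 1.0 | 10% vs 25% | 18% vs 30% |
| 10%, 40%, 0.7 | 10% vs 18.6% | 18% vs 32.6% |
| 20%, 20%, 1.0 | 20% vs 20% | 16% vs 32% |
| 40%, 10%, 1.0 | 40% vs 25% | 12% vs 30% |

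First row: (0.2×0.10 + 0.2×0.40)/0.4 = 25%, and 0.2×0.90 + 0.2×0.60 = 30%. With no drug effect on relapse, the clearers-only contrast makes PSL look worse (row 1), equal (row 3) or better (row 4), according to how the extra clearers relapse. With rE = 10%, rH from 30% to 50% and HR from 1.0 to 0.5, PSL relapse among clearers runs from 10.7% to 30.0% against 10% on placebo.

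**Step 3: what presentation by stratum does.** Let relapse depend on baseline load L (log10) only and not on arm: weekly hazard h = 0.02·exp(0.6(L − 3.5)), 12-week risk 1 − exp(−12h). Clearance is logistic and falls with L, with intercepts set so that 58% clear on PSL and 26% on placebo. Strata are split at an assumed 10,000 copies/mL. Load is either uniform in log10 over the eligible range, or normal (mean 4, SD 1.2) truncated to it. Entries are 12-week relapse among clearers, PSL vs placebo, with the gap in points.

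| Load distribution, logistic slope | Pooled | Low stratum | High stratum |
|---|---|---|---|
| Uniform, 1.0 | 33.9% vs 27.3% (6.6) | 19.1% vs 18.5% (0.6) | 48.0% vs 44.1% (3.9) |
| Uniform, 1.5 | 31.3% vs 23.5% (7.8) | 19.1% vs 18.3% (0.8) | 44.8% vs 39.8% (5.0) |
| Normal, 1.0 | 28.1% vs 25.0% (3.1) | 19.8% vs 19.2% (0.6) | 39.6% vs 38.1% (1.5) |
| Normal, 1.5 | 26.4% vs 22.6% (3.8) | 19.8% vs 18.9% (0.9) | 37.7% vs 36.0% (1.7) |

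A pooled gap of about 3 to 8 points falls to about 1 point in the low stratum and about 2 to 5 in the high stratum. This is the favourable case for stratification, because load is the only prognostic factor in the model. Selection on anything else, such as immune status, would pass through the strata.

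**Step 4: the trial's size.** Under the first row of Step 2, expected clearers are 0.4×40 = 16 on PSL and 0.2×20 = 4 on placebo. In 10,000 simulated trials of that size, the relapse rate among clearers was higher on PSL in 81% with no drug effect on relapse and in 72% with a true HR of 0.7. With equal relapse in both kinds of patient (row 3) it was 55%. Sampling noise is therefore large beside the bias.

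**The case against.** The strongest reply is that this is a minor descriptive display with safeguards around it. Most of that reply stands.

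- **Descriptive and exploratory.** Protocol 9.1 plans no formal testing, Protocol 9.4.4 has exploratory endpoints summarized descriptively, and the SAP specifies Kaplan-Meier summaries only. The tests in Protocol 9.4.5 do not name remission duration. This stands, and it limits the importance of the point.
- **Stratified display.** Splitting by screening load acts on the most obvious source of imbalance, and Step 3 shows a real reduction. It is incomplete: there are two strata over a wide range of loads, and one may hold as few as 6 patients, about 6/3 = 2 per arm.
- **Companion measures.** Time to resolution from randomization, resolution by visit (including Week 24) and at any visit, recrudescent infection by visit, and time-adjusted viral-load AUC are not conditioned on clearing. Resolution at Week 24 comes close to what is needed. None reports who cleared and stayed clear among all randomized patients; resolution at any visit also counts a patient who cleared once and relapsed.
- **Unequal remaining follow-up.** A reader might infer that later clearing on one arm is itself a bias. It is not if censoring is non-informative, because Kaplan-Meier handles it. The issue is who is in each group.

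A reader might also infer that the analysis will make PSL look worse. The documents do not support that. It requires the extra PSL clearers to relapse sooner, and no clearance or relapse rate by load is given. Step 2 shows that the contrast can also be neutral or flatter PSL.

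**Conclusion.** The point holds in limited form. By-arm curves of remission duration among clearers have no randomized interpretation, and the SAP lists them under a PSL-versus-placebo comparison without saying so. That conclusion follows from the text and needs no assumed rates.

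The direction and size of any bias are unknown. The illustrative gaps (3 to 8 points pooled, about 1 to 5 within strata) rest on assumed clearance of 58% and 26%, an assumed relapse hazard, assumed load distributions and an assumed stratum cut. They vanish if the extra clearers relapse like the others.

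The primary safety analysis and the key secondary change in viral load do not depend on this endpoint. This is a worthwhile, inexpensive improvement and not a flaw in the trial's main conclusions.

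**What to change.** Make the between-arm durability summary an all-randomized (ITT) one, by arm and with a 95% CI, using one or both of:
- the proportion of randomized patients who cleared and remained below LLOQ through Week 24;
- days in remission through Week 24, with 0 for patients who never cleared.

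State a rule for dropouts and missed visits, since SAP 3.1.5 otherwise leaves data as observed. One option is to count them as not sustained, with an observed-data sensitivity analysis. State also which confirmation rule ends a remission: SAP 2.3.3 asks for two measures at least 2 weeks apart, SAP 3.4.2 for at least 8 days.

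Keep the responder-only Kaplan-Meier curve and label it descriptive among clearers, not a randomized comparison. It still describes how long observed remissions last. The all-randomized measure combines clearing with staying clear, so it does not isolate durability, but its comparison is protected by randomization.

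The cost is a few table rows by arm and stratum and one missing-data rule. BK viral load is already scheduled through Week 24, so no new data are needed.

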9.2 Sample Size Determination

Note: “Enrolled” patients are those who have been randomized to a treatment arm.

No formal sample size determination was made for this study, whose primary endpoint is safety and tolerability. Approximately 60 patients will be randomized at approximately 38 clinical sites. Patients (n=20 in each arm) will be randomized to receive PSL [REDACTED] or placebo. [REDACTED]

Sample size estimates are based on a one-sided test at the 0.05 level to detect suppression of viral load to undetectable levels based on the viral load data from the CHARMS study of multivirus-specific T cells for patients with a plasma BK viral load <2000 copies/mL.

Patients will be stratified by screening BK viral load at randomization to ensure equal randomization among active and placebo arms for patient populations [REDACTED]
[REDACTED]

[REDACTED] A minimum of 6 patients must be enrolled in each stratum, but the remaining patients can be enrolled in either stratum.

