3.1.5 Handling of Dropouts and Missing Data

In general, data will be analyzed and presented as observed and will not be imputed for the analysis of efficacy and safety, unless otherwise specified.

In case the start and end dates for adverse events and concomitant medications/procedures are missing or incomplete, the missing component(s) will be assumed as the most conservative value possible. For example, AEs with missing start dates, but with stop dates either overlapping into the treatment period or missing, will be counted as treatment-emergent, taking the worst-case approach. When partial dates are present in the data, both a partial start date and/or a partial stop date will be evaluated to determine whether it can be conclusively established that the AE started prior to the start of study treatment or ended prior to the start of study treatment. If the above cannot be conclusively established based on the partial and/or present dates, then the AE will be considered as treatment-emergent. Actual data values as they appear in the original case report forms (CRFs) will be presented in the data listings.

Viral load values below the limit of quantification will be imputed as the limit of quantification minus 0.1 unit (for CMV) or minus 1 unit (for other viruses).

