3.4.1 Secondary Efficacy Endpoints

The key secondary efficacy endpoint is change from Baseline in BK viremia in both copies/mL and log10 copies/mL in patients receiving PSL (pooled PSL) compared to patients receiving

placebo, based on quantitation of viremia performed at the central laboratory. The other secondary efficacy endpoint is change in BK viremia in patients receiving different dosing regimens of PSL compared to patients receiving placebo in copies/mL and log10 copies/mL. Change in BK viremia will be assessed by BK viral load assessments.

Observed, change from baseline and percent change from baseline values for BK viral load will be summarized by visit and treatment using descriptive statistics. Percentage change of BK viral load from baseline at each post baseline visit will be presented to determine the rate of decline of BK viremia. Listing will be provided for BK viral load.

AUC for BK viral load (in log 10 copies/ml) adjusted by time duration (area divided by days) will be summarized at each post-baseline timepoint by treatment arm using descriptive statistics. Listings will be provided for AUC of BK viral load.

Two different plots of BK viral load and change from Baseline (both copies/mL and log scale) will be presented for both mean+/- SD and median & IQR by visit for (Arm 1, Arm 2 and Arm 3) and (Arm 1+2 and Arm 3).

Two sets of figures will be produced for mean+/- SD for percent change from baseline (day 1) for BK-viral load for (Arm 1, Arm 2 and Arm 3) and (Arm 1+2 and Arm 3).

Two sets of figures will be produced for both mean+/- SD and median & IQR for AUC for (Arm 1, Arm 2 and Arm 3) and (Arm 1+2 and Arm 3).

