Time to resolution of non-BK target viral infections (i.e., associated signs, symptoms, and presence/absence of CMV, HHV-6, EBV, JCV, and/or AdV viremia) will not be performed due to limited number of events for each virus. The time to death will not be performed but the deaths will be summarized and listed.

To evaluate the impact of missing data at some timepoints, a sensitivity analysis will also be performed on BK viremia using last observation carried forward imputation.

In addition, the number and percentage for patients will be presented for following endpoints by visit unless otherwise stated.

- Patients with eGFR >20 mL/min/1.73m² at 24 weeks
- Patients with incidence of new target viral infections or recrudescent infections (i.e., BKV, CMV, EBV, AdV, JCV, and/or HHV-6) as defined by onset of viremia.
The associated symptoms are not collected so will not be considered.
- Patients with screening BK viremia <10,000 copies/mL who develop BK viremia \geq 10,000 copies/mL (sustained or non-sustained) or who experience reduction of immunosuppression which is defined as a reduction of 50% or greater of the current dose when compared to the dose at Baseline for the following medications: tacrolimus, Prograf, Envarsus, cyclosporine, Neoral Sandimmune, everolimus, sirolimus, Rapamune, rapamycin, mycophenolate mofetil, mycophenolate sodium, mycophenolic acid, Cell Cept, Myfortic, azathioprine).
 - The following drugs would not be considered for immunosuppression reduction: Prednisone, methylprednisolone, glucocorticoids, Leflunomide, Arava, Gammagard or IVIG.

Two sets of figures will be produced for mean+/- SD for change from baseline for eGFR for (Arm 1, Arm 2 and Arm 3) and (Arm 1+2 and Arm 3).

Two sets of figures will be produced for mean+/- SD for change from baseline for Creatinine for (Arm 1, Arm 2 and Arm 3) and (Arm 1+2 and Arm 3).

Listings will be provided for viral loads, eGFR, creatinine, HLA related information and donor specific anti-HLA antibodies.

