3.5.2 Clinical Laboratory Tests

Laboratory assessments comprise safety laboratory tests (hematology, clinical chemistry and urinalysis) and other laboratory tests.

Descriptive statistics will be provided for clinical laboratory test results (hematology, clinical chemistry and routine urinalysis) and changes from baseline. With the exception of the LOCF sensitivity analysis of BK viremia, missing values for any of the laboratory evaluations will not be imputed; that is, only observed case data will be used.

A shift table, presenting the 2-way frequency tabulation for baseline and the worst post-baseline value according to the NCI CTCAE grade, will be provided for clinical laboratory.

In addition, the number and percentage of patients with the following potentially clinically significant abnormal liver function tests will be summarized:

- Potential Hy's Law cases: ALT or AST $\geq 3 \times \text{ULN}$ and total bilirubin $\geq 2 \times \text{ULN}$ and Alkaline phosphatase (ALP) $< 2 \times \text{ULN}$.

Listings will be presented for all laboratory data and all test values outside the normal range will be flagged.

In addition, other laboratory tests, including pregnancy test, serology test, testing for HIV, HCV, HBV and CMV, and donor specific anti-HLA antibodies will be presented in by-patient listings.

3.5.3 *Vital Signs*

Descriptive statistics will be provided for vital signs (including blood pressures, pulse rate, respiratory rate, oximetry, and body temperature), body weights, and BMIs by treatment group at each scheduled visit. Changes from baseline will also be summarized.

All vital sign data will be listed by patient.

3.5.4 *Electrocardiograms*

ECG measurements include heart rate (bpm), measures PR (msec), QRS (msec), QT (msec), and QTc (msec) (corrected using Fridericia's and Bazett's methods). Descriptive statistics will be provided for the observed measurements and change from baseline.

All ECG parameters and the Investigator interpretation of findings including details of any abnormalities will be listed by patient.

3.5.5 *Physical Examinations*

All abnormal physical examination findings, including details of any abnormalities will be listed by patient.

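### Last observation carried forward, the only planned sensitivity analysis for missing BK viral loads, is a weak check on the observed-case summary

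*SAP*

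**What the plan says.** SAP 3.1.5 sets the general rule: "data will be analyzed and presented as observed and will not be imputed". SAP 3.4.1 applies it to the key secondary endpoint with by-visit summaries and no model: "Observed, change from baseline and percent change from baseline values for BK viral load will be summarized by visit and treatment using descriptive statistics".

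SAP 3.4.2 then adds one analysis aimed at missing values: "a sensitivity analysis will also be performed on BK viremia using last observation carried forward imputation". SAP 3.5.2 confirms that nothing else is imputed: "With the exception of the LOCF sensitivity analysis of BK viremia, missing values for any of the laboratory evaluations will not be imputed".

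Two other rules touch BK data but do not address missing change values:

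- SAP 3.1.5 replaces results below the quantification limit (156 copies/mL for BK virus, so 155). This concerns the assay, not absent samples.
- SAP 3.4.2 handles early leavers in time to resolution and time to reappearance by censoring: each "will be censored at the last assessment date for this endpoint".

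No mixed model, multiple imputation or delta analysis is named. The SAP does not say which visits or summaries LOCF covers (change, time-adjusted AUC, resolution by visit) or whether a baseline value may be carried forward.

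**The concern.** LOCF treats the last sample as the patient's true value at every later visit. The documents give three reasons to expect otherwise:

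- Immunosuppression reduction is allowed in every arm (Protocol 6.8) and is described as lowering BK load (Protocol 4.2).
- Protocol 4.1 and 6.8 anticipate that it may be needed less often on posoleucel (PSL) than on placebo, so the course over time can differ by arm.
- Dosing ends after Week 12 and follow-up runs to Week 24 (Protocol 6.6). Reappearance of viremia is itself an endpoint. A patient who clears the virus and then leaves would be carried as cleared to Week 24.

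Some missing data are foreseeable. Withdrawn patients are not replaced (Protocol 7.2), and an unblinded patient must leave the study (Protocol 6.3).

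At stake is the robustness check on the key secondary endpoint. LOCF can show a difference that does not exist or hide one that does. It also leaves untested the assumption on which the observed-case means rest.

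**Working it through.** **Inputs from the documents.** "Approximately 60 patients will be randomized at approximately 38 clinical sites" (Protocol 9.2), 20 per arm in three arms: 3 × 20 = 60, or 40 pooled PSL against 20 placebo. BK load is drawn on Day 1 and then at 12 two-weekly visits from Day 15 to Day 169. The plan gives no figure for dropout, SD or trend, so there is nothing to reproduce on those.

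**Assumed inputs.** Both arms have the same true fall D in log10 load by Week 24. Dropout is unrelated to outcome, and a leaver's last sample is equally likely to be any of the 12 visits before Week 24, Day 1 included.

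**Step 1: share of the fall not yet reached at the last sample (m).**
- Linear fall: m = 1 − (0 + 1 + … + 11)/(12 × 12) = 1 − 66/144 = 0.542.
- Linear fall to Week 12, then flat: m = 1 − (15/6 + 6)/12 = 1 − 8.5/12 = 0.292.

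**Step 2: LOCF artefact at Week 24.** The LOCF mean in an arm with dropout d is −D(1 − d·m). The difference, PSL minus placebo, is therefore −(d_placebo − d_PSL) × D × m. The true difference is zero.

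| Dropout, placebo vs PSL | D = 1, linear | D = 1.5, linear | D = 2, linear | D = 1, plateau |
|---|---|---|---|---|
| 10% vs 10% | 0 | 0 | 0 | 0 |
| 20% vs 10% | −0.054 | −0.081 | −0.108 | −0.029 |
| 30% vs 10% | −0.108 | −0.162 | −0.217 | −0.058 |
| 40% vs 10% | −0.163 | −0.244 | −0.325 | −0.088 |

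Seven of the nine unequal-dropout linear cells lie between 0.05 and 0.22. With D = 0 every cell is zero. Swapping the dropout rates reverses the sign.

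**Step 3: simulation.** 40 PSL vs 20 placebo, linear fall, assumed slope SD 0.6 and residual SD 0.3, 5,000 runs, one-sided t test at 0.05.

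| D; placebo vs PSL dropout | LOCF difference | LOCF rejection rate | Observed-case difference |
|---|---|---|---|
| 1; 10% vs 10% | 0.002 | 0.051 | 0.002 |
| 1; 20% vs 10% | −0.049 | 0.079 | 0.004 |
| 1; 30% vs 10% | −0.107 | 0.127 | 0.003 |
| 1; 10% vs 30% | +0.106 | 0.014 | −0.003 |
| 1.5; 30% vs 10%, all dropout early | −0.273 | 0.315 | 0.002 |
| 0; 30% vs 10%, all dropout early | 0.004 | 0.046 | 0.006 |

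The simulation agrees with Step 2. Observed-case rejection stayed between 0.045 and 0.056, as it should when dropout is completely random. Outcome-related dropout was not simulated.

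**Step 4: assay floor.** Results below 156 are set to 155. A patient entering at the minimum of 350 copies/mL can fall by at most log10(350/155) = 0.35. A 1 log10 fall needs a start of at least 155 × 10 = 1,550, and a 2 log10 fall at least 15,500. Patients near the floor contribute less artefact than the table shows.

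**The case against.** The case for leaving the plan alone is substantial.

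- **LOCF is secondary.** The main summary is observed-case. In the scenarios above that summary is unbiased and only the LOCF run moves. A reader might infer that the trial's viral load result is itself distorted, or that agreement between the two analyses has been shown to mislead. Neither is supported: in these scenarios the two disagree. A case where both agree and both are wrong would need outcome-related dropout, which has not been quantified.
- **The analysis is descriptive.** Protocol 9.1 rules out formal testing, and SAP 3.4.1 gives summaries and plots. A reader might infer an inflated false-positive rate from Step 3. That applies only if the one-sided t test in Protocol 9.4.5 is run on BK load, and whether it will be is a separate inconsistency to resolve.
- **Dropout may be low.** Patients who stop infusions stay in follow-up (Protocol 7.1), including those who stop after clearance (Protocol 6.5.1), so that rule does not itself create missing data. Home visits are allowed, and Week 24 assessments are sought from early leavers (Protocol 7.2). In arms of 20, 10% against 30% means 2 patients against 6.
- **Some gaps are single missed visits.** At a 1 log10 fall over 24 weeks, carrying one value forward shifts that patient by 1/12 = 0.08 log10, at that visit only.
- **Other BK endpoints handle early leavers by censoring.** A reader should not take LOCF as the only provision for dropout anywhere in the BK analyses. It is the only one for missing load values.
- **A model has its own difficulties.** An unstructured covariance over 12 visits has 12 × 13/2 = 78 parameters in about 60 patients, and values piled at 155 strain normality.

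All of these points stand, and they limit the weight of the concern. None of them makes a frozen load a suitable assumption, and none supplies a check on outcome-related dropout.

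**Conclusion.** The concern holds in a limited form. LOCF is a poor sensitivity analysis here because its assumption conflicts with how the documents expect BK load to behave. When load is falling and dropout differs, it produces a difference between identical arms. Under the assumed inputs the size is about 0.05 to 0.2 log10 in most cases, up to 0.33 in the most extreme cell of the linear table, and about half as large with a plateau at Week 12. It is zero without a trend or with equal dropout. All of these figures rest on assumed dropout, trend and timing.

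A reader might take this as a bias in favour of PSL. The documents do not support that, because the direction depends on which arm loses more patients and nothing in them says which that will be.

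Observed-case means are unbiased under completely random dropout but not in general when leaving depends on viral load or its course. LOCF does not probe that. This is a worthwhile, inexpensive improvement and not a flaw that undermines the trial.

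**What to change.** Before the SAP is finalized, in SAP 3.4.2:

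1. Replace LOCF, or demote it to a supplement, with a repeated-measures model on log10 BK load. Include treatment, visit, treatment by visit, baseline log10 load and stratum, under missing at random.
2. Prespecify the covariance structure and a simpler fallback if it does not converge.
3. Treat values below the quantification limit as censored, or check how far results depend on the substituted 155.
4. Add a delta-adjusted multiple imputation run for patients who leave early, over a range of deltas stated in advance.
5. Report estimates descriptively, in keeping with the rest of the SAP.
6. If LOCF stays, state which visits and summaries it covers and whether baseline may be carried forward.

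Amend the LOCF exception in SAP 3.5.2 to match. The cost is SAP wording, modest extra programming, and a model-based estimate in an otherwise descriptive plan. Sample size and data collection do not change.
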